5.2 Escape medication (if applicable)

The participant and their treatment team are asked not to start any other form of traumafocused treatment, to refrain from offering cognitive behaviour therapy for psychosis, and to keep medications unchanged up to the 6-month follow-up. However, in the case of adverse events or increases in symptoms of psychosis that demand intervention, antipsychotics, sedatives or CBT may be increased or provided.

6. METHODS

6.1 Study parameters/endpoints

6.1.1 Main study parameter/endpoint

Researcher-rated changes in severity of PTSD symptoms on the CAPS between baseline and 6-month follow-up.

6.1.2 Secondary study parameters/endpoints (if applicable)

Changes in the number of participants fulfilling the diagnostic criteria of PTSD, self-rated severity of PTSD symptoms and severity of complex PTSD symptoms, posttraumatic cognitions, dissociation, depression symptoms, paranoia, auditory verbal hallucinations, social functioning, disruption of social functioning by PTSD symptoms, resilience, personal recovery, sexual functioning, adversities, and revictimization in the period between baseline and 6-month follow-up.

6.1.3 Other study parameters (if applicable)

12-month and 24-month follow-up outcomes for the primary and secondary study parameters in the PE, EMDR and CR conditions. Since the WL group is not assessed at 12 and 24-month follow-up, these comparisons are within group, i.e. 12 and 24-month follow-up outcomes are compared with the 6-month follow-up data for each arm. Cost-effectiveness of PE, EMDR and CR compared to WL between baseline and 6-month follow-up. Potential baseline predictors are PTSD, complex PTSD, paranoid ideation, negative impact of voices and social support. The baseline and post-treatment assessment will be augmented by daily monitoring to study how post-traumatic stress and psychosis symptoms dynamically interact and how treatment affects these dynamic interactions (see daily monitoring below).

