2. OBJECTIVES

Primary Objective:

Our primary objective is to test the effects on researcher-rated severity of PTSD symptoms of a full dose of prolonged exposure therapy (PE), eye movement desensitization and reprocessing therapy (EMDR), cognitive restructuring therapy without direct trauma memory processing (CR), and waiting list (WL). We will compare all arms and are primarily interested in comparing the active treatments (PE, EMDR and CR) to WL, and in comparing the interventions with (PE and EMDR) to the intervention without (CR) direct memory processing.

Secondary Objectives:

Second, we aim to investigate the effects of PE, EMDR, CR, and WL on researcher-rated presence of PTSD diagnosis, self-rated severity of PTSD symptoms and severity of complex PTSD symptoms, posttraumatic cognitions, dissociation, depression symptoms, paranoia, auditory verbal hallucinations, social functioning, disruption of social functioning by PTSD symptoms, experienced resilience, personal recovery, sexual functioning, adversities, and revictimization. Third, with the long follow-up we aim to test the long-term effects on all the outcomes for the first time. Fourth, we aim to explore how post-traumatic stress and psychosis interact dynamically, how the experimental treatments influence these interactions, and what factors significantly predict treatment response. Our fifth aim is to determine the cost-effectiveness of the interventions. Sixth, we will conduct a process evaluation of the therapy process by conducting interviews in a subgroup of participants to examine how they experienced receiving trauma-focused treatment.

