3. STUDY DESIGN

A single-blind multicentre randomised controlled trial with four arms: PE, EMDR, CR, and WL. All groups receive treatment as usual for psychosis. All the groups will be assessed at baseline (T0), mid-treatment (T1), posttreatment (T2), and at 6-month follow-up (T3). These assessments will take about 90 minutes to administer. Participants in the WL condition can choose to undergo treatment of choice after the 6-month follow-up assessment. The PE, EMDR and CR conditions will also be assessed at 12-month and 24-month follow-up. Up to the 6-month follow-up assessment, all groups weekly monitor the outcomes social functioning, adversities, and revictimization. Participants in the active treatment arms will receive two treatment sessions per week.

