5.1 Investigational product/treatment

Prolonged exposure therapy (PE)

In the first session, the therapist delivers normalizing psycho-education and together with the participant develops a case formulation and treatment plan. The therapist informs the participant about trauma, PTSD and the many negative consequences that trauma can have on our lives, including symptoms of psychosis. In collaboration with the participant, the therapist develops a case formulation that contains the most important traumatic

experiences, a hierarchy of the most relevant trauma memories based on subjective units of distress scores (SUD) and frequencies of intrusions, the experience of psychosis and associated memories, the most important avoidance behaviours, the most important strengths of the person, and associations between these factors. The participants then receive 7 sessions in which re-experienced traumatic memories associated with PTSD symptoms are processed and in which exposure in vivo is done on trauma-related stimuli that are avoided. After the mid-treatment assessment (T1), participants will receive a maximum of 8 additional sessions in the second phase of treatment. The first session of the second phase starts with evaluating and updating the case conceptualisation, the treatment plan, and the treatment/recovery goals. The therapist also explains the rationale for the second phase of treatment. In this second phase additional trauma memories associated with PTSD will be processed. If PTSD comes into remission, therapists are allowed to process traumatic memories that are associated with psychosis symptoms in the absence of PTSD re-experiencing. The exact number of sessions that are delivered is based on predetermined completion criteria: i.e. symptoms of PTSD are in remission for at least two consecutive sessions (the participant scores 0 on sections B – reliving - and C – avoidance - of the PCL-5), there are no more traumas that are associated with PTSD on the hierarchy with a SUD > 0, and there are no more psychosis related memories or imagery with a SUD > 0) and a shared decision-making process between participant and therapist.

The PE therapy will be delivered conform the protocol of Foa, Hembree and Rothbaum (2007).⁵² This protocol consists of imaginal exposure (whereby each session is audio recorded and participants listen to these recordings five times per week) and in vivo exposure (based on a list of avoided trauma-related stimuli).

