If a treatment is found to be effective, cost-effectiveness analyses will be performed. The incremental cost-effectiveness ratios (ICERs) are considered to be a single-point estimate of an underlying continuum. Acceptability curves are produced with bootstrap simulations and confidence intervals. The outcome will be costs in Euro's per QALY and the costs in Euro's per day without PTSD gained. If none of the treatments are effective, which is not expected, a cost-minimization calculation will be performed. Inductive

Thematic Analysis will be used to analyse themes in the views of participants TFT and the process of recovery.^{81,82}

The trial is deemed successful when we have included enough participants to carry out all above-mentioned analyses and answer all hypotheses.

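### The 6-month cost-effectiveness analysis is specified against waiting list only; add a four-option incremental analysis so that a therapy dominated by another is seen to be dominated

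*Protocol*

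**What the plan says.** The only sentence in the protocol that names a comparator for the economic evaluation is in Section 6.1.3: "Cost-effectiveness of PE, EMDR and CR compared to WL between baseline and 6-month follow-up".

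The analysis itself is in Section 8. It is conditional on a clinical result ("If a treatment is found to be effective, cost-effectiveness analyses will be performed"). It rests on ratios ("The incremental cost-effectiveness ratios (ICERs) are considered to be a single-point estimate of an underlying continuum"), with uncertainty shown as follows: "Acceptability curves are produced with bootstrap simulations and confidence intervals". The outcome measures are also given: "The outcome will be costs in Euro's per QALY and the costs in Euro's per day without PTSD gained". Section 8 names no economic comparator, does not order the options by cost, has no dominance step, and does not say whether the acceptability curves are pairwise or cover all options together.

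The design is "A single-blind multicentre randomised controlled trial with four arms: PE, EMDR, CR, and WL". Section 2 states a primary interest in comparing the active treatments with WL and also "in comparing the interventions with (PE and EMDR) to the intervention without (CR) direct memory processing". The fifth aim there is the cost-effectiveness of the interventions, with no comparator named.

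**The concern.** PE, EMDR and CR are alternatives: a participant is allocated to one of them or to WL. Someone deciding what to fund therefore chooses among four options. A ratio against WL shows whether a therapy is worth adding to usual care. It does not show whether a second therapy gives more benefit for the same or less money, because the second therapy does not enter the ratio. Two therapies can both fall below a threshold against WL while one dominates the other.

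The clinical part of the trial is built to separate the therapies, and the economic part as worded does not carry that comparison over. At stake is how useful the fifth objective is: a therapy could be reported as cost-effective when a cheaper and better one was tested beside it in the same trial.

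**Working it through.** **1. The plan's own figures.** The protocol gives no numerical result or threshold for the economic analysis. The one usable cost input is the treatment line in Appendix 3: 180 participants × 18 treatments × EUR 196 = EUR 635,040, which reproduces as stated. The 18 contacts agree with Section 5: at most 16 sessions, plus one meeting before and one after. Per participant this is 18 × 196 = EUR 3,528. With 14 contacts it would be 14 × 196 = EUR 2,744.

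**2. Can a dominated therapy pass against WL?** From the protocol: the unit cost of EUR 196. Assumed: the contact numbers per therapy, the QALY gains, the threshold λ, and no cost difference from WL other than the therapy itself.

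ICER against WL = ΔC / ΔQ. Net benefit against WL = λ × ΔQ − ΔC.

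| Therapy | Contacts | ΔC (EUR) | ΔQ (QALY) | ICER against WL (EUR) | Net benefit at 80,000 | at 50,000 | at 20,000 |
|---|---|---|---|---|---|---|---|
| A | 14 | 2,744 | 0.08 | 34,300 | 3,656 | 1,256 | −1,144 |
| B | 18 | 3,528 | 0.06 | 58,800 | 1,272 | −528 | −2,328 |

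At EUR 80,000 both therapies pass against WL. Against each other, B costs 3,528 − 2,744 = EUR 784 more and yields 0.08 − 0.06 = 0.02 QALY less, so B is dominated. An incremental analysis removes it.

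Range: at EUR 3,528, B passes against WL once its gain exceeds 3,528 / λ. That is 0.044 QALY at EUR 80,000, 0.071 at EUR 50,000 and 0.176 at EUR 20,000. None of these limits depends on therapy A.

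**3. What the probabilities look like.** Inputs: 50 per arm (Section 4.4) and EUR 3,528 per therapy. Assumed: QALY SD 0.097, cost SD EUR 5,000, costs and QALYs uncorrelated, and normally distributed arm means.

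- The standard error of an arm's mean net benefit at λ = 80,000 is √[(80,000 × 0.097)² + 5,000²] / √50 = 9,231 / 7.071 ≈ EUR 1,305. For a difference between two arms it is 1,305 × √2 ≈ EUR 1,846.
- Equal gains of 0.06 for all three: net benefit 80,000 × 0.06 − 3,528 = 1,272, and Φ(1,272 / 1,846) ≈ 75% for each therapy against WL. In 400,000 simulated draws each therapy is the best of the four with probability 31%.
- Gains of 0.07, 0.07 and 0.05 for PE, EMDR and CR: CR has net benefit 472, so Φ(472 / 1,846) ≈ 60% against WL. PE and EMDR have 2,072, so Φ(2,072 / 1,846) ≈ 87% against WL. CR is the best of the four with probability 8%.
- Same gains, with PE and EMDR at 14 contacts: PE and EMDR 94% each and CR 60% against WL. CR is best with probability 3%.
- Same gains, equal costs, lower thresholds: at λ = 50,000 CR is 23% against WL and about 6% as best option. At λ = 20,000 CR is about 1% against WL.
- Varying the QALY SD from 0.06 to 0.15 and the cost SD from EUR 2,500 to 10,000 at λ = 80,000, with equal costs, keeps CR at 56–67% against WL and 2–14% as best option.

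The probability of being cost-effective against WL and the probability of being the best of four are thus answers to different questions. The wording of the protocol points to the first and does not commit to the second.

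**The case against.** The case on the other side is substantial, and much of it stands.

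- **WL is a legitimate comparator.** All arms receive usual care, and Section 2 lists the active treatments against WL first among the comparisons of main interest. Whether a therapy is worth adding to usual care is a proper question. This stands, so the WL comparisons should be kept.
- **The ranking can be recovered.** A reader might infer that the analysis cannot say which therapy to fund, or that it will endorse the wrong one. That goes too far. Because WL is shared, ordering the therapies by net benefit against WL is the same as ordering them against each other; in the illustration, PE and EMDR at 87% beside CR at 60% already shows the order. Subtracting incremental costs and effects also gives the contrasts between therapies. What remains is that a bare ratio does not display dominance, and the protocol does not commit to net benefit or to these contrasts. Pairwise probabilities that sum to more than 1 are normal and are no error.
- **Section 8 leaves room.** It does not exclude a multi-option acceptability curve, and Appendix 4 plans cost-effectiveness at 12 and 24 months, when WL is no longer assessed. But for 6 months, where all four arms have data, the one stated comparator is WL. That is a choice the protocol makes, not merely a detail left open.
- **Therapy costs may not differ.** Under PE, Section 5.1 says "The exact number of sessions that are delivered is based on predetermined completion criteria", and EMDR follows the same procedures. A reader might infer that PE and EMDR will be cheaper than CR. Section 5 sets the same maximum of 16 sessions for all three, so 14 against 18 contacts is only an assumption. The point does not need it: at equal cost, a less effective therapy is still dominated.
- **Confidence intervals.** A reader might infer that intervals are to be placed on the ICERs. Section 8 mentions them together with the bootstrap and the acceptability curves, so no criticism on that ground is made.

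**Conclusion.** The point holds as a gap in the specified economic comparison. Section 6.1.3 fixes WL as the only comparator at 6 months, and nothing in Section 8 adds an economic comparison among PE, EMDR and CR. A dominated therapy could therefore be reported as cost-effective.

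The size cannot be fixed from the protocol. The illustrations rest on assumed QALY gains, standard deviations, contact numbers and thresholds; only the EUR 196 unit cost, the 18 budgeted contacts and the 50 per arm come from it. The misleading result appears at EUR 80,000 with the assumed gains and largely disappears at EUR 50,000 and below. The primary outcome and the sample size are not affected. This is a cheap improvement to a secondary aim, not a flaw that invalidates the economic evaluation.

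**What to change.** In Sections 6.1.3 and 8, keep the comparisons of PE, EMDR and CR with WL and add one four-option incremental analysis over baseline to 6 months, from the same bootstrap samples:

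- order WL, PE, EMDR and CR by mean cost;
- remove dominated options, and those extendedly dominated (an option whose ICER against the next cheaper option is higher than that of a more effective, more costly option);
- give each remaining option's ICER against the next remaining option;
- show one acceptability plot with the probability that each of the four has the highest net benefit, over a range of thresholds;
- report the incremental net benefit of PE and of EMDR against CR, to match the clinical comparison in Section 2.

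The cost is a change of wording and a little more analysis. Data, visits, sample size and bootstrap stay as they are. The downside is that the probability reported for any single therapy will be lower than its probability against WL alone.

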6.2 Randomisation, blinding and treatment allocation

Randomization is conducted via a scientific randomization program on the Internet (http://www.randomizer.org) by the independent randomization bureau of Parnassia Psychiatric Institute. All trial therapists will provide all treatments. There will be 50 lots for each of the arms. These lots will be divided in proportion over the participating therapists. All research assistants are blind for treatment allocation. In case of incidental unblinding, another research assistant will perform the rest of the assessment.

Version number: 2.0, date 15-02-2019

6.3 Study procedures

Participating mental health organisations will refer eligible patients with a psychotic disorder in the schizophrenia spectrum (confirmed by the responsible clinician with the Structured Clinical Interview for DSM-5) and a suspicion of PTSD to the study. Trial therapists will inform patients with psychosis that they suspect to have comorbid PTSD about the study. If a patient is interested, the therapist asks for written permission to provide the (contact) details of the patient to the researchers. The patient will then be contacted by a researcher and informed about the study both verbally and in reading. Patients then receive at least one week to consider participation in the study. If patients decide to participate, they are invited for a faceto-face meeting in which they can ask additional questions about participation, informed consent is obtained and in which inclusion criteria and exclusion criteria are assessed. When patients meet all inclusion and no exclusion criteria, they will undergo the T0 baseline assessment and will then be randomised. They will be instructed how to perform the web-based assessments and are provided a smartphone and sim-card if they don't own one. All participants will be invited by their allocated trial therapist who will inform them about the allocated study arm, set up a schedule for the treatment sessions, and start with the therapy. Up to the 6-month follow-up assessment participants weekly monitor the outcomes social functioning, adversities, and revictimization, since these factors may be more difficult to estimate in hindsight and may be more susceptible to memory bias. Seven weeks after baseline, the mid-treatment assessment (T1) will be performed. Then the second treatment phase will start, after which participants will undergo the posttreatment assessment (T2) at week 13, and later the 6-month follow-up assessment (T3). All assessments are done by researchers from the VU/Parnassia. They travel to the institution where the participant receives treatment and collect the data through the online data-management program Castor. Participants in the WL condition can choose to undergo their TFT of choice after the latter assessment. The PE, EMDR and CR conditions will also be assessed at 12-month and 24-month follow-up.

All interviews and assessments take place at locations of the participating mental health organisation, ideally the location that the patient regularly attends for treatment.

Instruments

TABLE 1 presents an overview of the instruments used.

Demographic characteristics: to determine demographics at recruitment. These include age, sex, cultural identity, education, employment, living condition, relationship status, duration of PTSD, duration of psychosis, duration of being in mental healthcare. Substance use is assessed using the first two questions of the Alcohol, Smoking and Substance Involvement Screening Test (ASSIST) that was developed for the World Health Organization (WHO).⁵⁵

TALE: to assess traumatic childhood experiences at recruitment.

The Trauma and Life Event Checklist (TALE) is a 21-item checklist for traumatic experiences and shocking life events in people with psychotic disorders that was recently developed.⁵⁶ It covers all main categories of trauma (abuse and neglect) and also bullying, stressful psychotic experiences, experiences of loss, and stressful experiences in contact with mental health or criminal justice services.

CAPS-5: to assess diagnosis of chronic PTSD at inclusion and as an outcome.

The Clinician-Administered PTSD Scale for DSM-5 (CAPS-5) is a valid and reliable measure with high specificity and sensitivity and is the gold standard diagnostic interview for posttraumatic stress disorder. The DSM-5 version has recently been validated and has good psychometric properties. With the CAPS-5 all DSM-5 symptoms are assessed and scored on intensity and frequency. The enumeration of those scores lead to a continuous severity score which will be used as the primary outcome of the study. Every symptom with a severity score > 2 is regarded as a clinically significant symptom. Using this cut-off it can be determined whether the criteria for a PTSS diagnosis are met. The CAPS-5 provides a symptom severity score and also assesses the presence of a PTSD diagnosis. The CAPS-5 will be administered by psychologists with a Msc. degree and Bachelor and Master students. They will be trained and monitored by a clinical psychologist with extensive experience in administering the CAPS-5.

PSYRATS: to assess auditory verbal hallucinations and delusions at recruitment.

The psychotic symptoms rating scales (PSYRATS) is an 18-item clinical interview that assesses delusions (The Delusion Rating Scale) and Auditory Hallucinations (The Auditory Hallucination Rating Scale, AHRS) and will be assessed at baseline. The PSYRATS scales were found to have excellent inter-rater reliability and to have strong validity. We slightly augmented the PSYRATS in that it also captures the type of delusions and hallucinations. At follow-ups we will assess only 3 items of the AHRS, i.e. frequency, duration, and disruption in order to capture intensity of voices.

ESSI: To assess social support at baseline (predictor).

The Enriched Social Support Instrument (ESSI) is a short 5-item measure of social support and was found to have good validity and reliability.⁶²

PCL-5: to assess self-rated severity of PTSD symptoms.

The PTSD Checklist for the DSM-5 (PCL5) is the most commonly used PTSD self-report questionnaire and has been validated in many different types of samples.⁶³ The DSM-5 version was recently found to demonstrate strong validity and reliability.⁴⁶ PCL-5 item scores are summed to yield a continuous PTSD symptom severity score.

ITQ: to assess complex PTSD.

The International Trauma Questionnaire (ITQ) is an 18-item self-report questionnaire that assesses the presence of complex PTSD as defined in the ICD-11 and includes an assessment of disruption of social functioning by PTSD symptoms.⁶⁴ Psychometrics have been tested and will be published shortly.

TSDQ-s: to assess dissociation.

The Trait State Dissociation Questionnaire – short version (TSDQ-s) is a 15 item self-report questionnaire that assesses dissociation. It was developed from existing dissociation measures (including the Dissociative Experiences Scale, Bernstein & Putnam, 1986 and the Peritraumatic Dissociation Scale, Marmar et al, 1994) and also included new items measuring aspects of dissociation which were not sufficiently represented in existing scales, particularly emotional numbing. The TSDQ-s has been shown to be psychometrically robust.⁴⁸

PTCI-9: to assess post-traumatic cognitions.

The Brief version of the Posttraumatic Cognitions Inventory (PTCI-9)⁴⁷ measures trauma-related cognitive distortions about the self, the world and about self-blame. This is a 9-item version is based on the original PTCI⁶⁵ and was found to have strong psychometrics.⁴⁷

BDI-II: To assess severity of depression at inclusion and as an outcome.

The Beck Depression Inventory II (BDI-II) is a widely used 21-item self-report for depression. It provides a continuous score for the severity of depression symptoms. The BDI-II has excellent psychometric properties.^{66,67}

GPTS: to assess paranoid ideation.

The Green et al. Paranoid Thought Scales (GPTS) assess ideas of persecution and social reference and were found to have good internal consistency. Validity was established for both scales. The scales were sensitive to clinical change. A hierarchical relationship between social reference and persecution was found.⁶⁸

VIS: assess the impact of auditory verbal hallucinations.

The Voice Impact Scale (VIS) is a 24-item self-report questionnaire that assesses the impact of voices. It contains three subscales: negative Impact of voices, positive impact of voices, and living well with voices. The psychometric qualities of the VIS are good. A publication concerning the psychometrics is under way.

BRS: to assess resilience.

The Brief Resilience Scale (BRS) is a 6-item questionnaire of resilience that was found to have good psychometric properties.⁶⁹

QPR: to assess personal recovery.

The 15-item questionnaire about the process of recovery (QPR) assesses personal recovery.⁴⁹ The QPR showed internal consistency, construct validity and Reliability.

ASEX and SAS: to assess sexual functioning.

The 5-item Arizona Sexual Experience Scale (ASEX) assesses sexual dysfunction. It measures the strength of sex drive, ease of sexual arousal, penile erection/vaginal lubrication, ability to reach orgasm and satisfaction with orgasm on a six-point scale, ranging from 1 (no impairment) to 6 (complete impairment). The ASEX total score ranges from 5–30, with higher scores representing greater sexual dysfunction. The ASEX scale is applicable with high validity and reliability to patients regardless of availability of a sexual partner and their sexual orientation. The sexual autonomy scale (SAS) consists of three items measuring the extent to which participants feel their sexual behaviors are self-determined. Participants are asked to indicate the extent of agreement-disagreement on a seven-point Likert scale. The range for the total score is 3–21. Higher scores represent higher levels of sexual autonomy.

TiC-P and EQ-5D: to assess cost-effectiveness and quality adjusted life years.

Care consumption list developed by Trimbos/iMTA for costs associated with psychiatric illness (TiC-P), short version.⁷² Questions from the Productivity and Disease Questionnaire – PRODISQ. The EuroQol (EQ-5D) is the World Health Organisation measurement for health outcome that can be expressed in utilities. Utilities can be combined with cost-effectiveness data into Quality Adjusted Life Years (QALYs).⁷³

Weekly monitoring: to assess the outcomes social functioning, adversities and revictimization in an ecologically valid way.

Once per week participants are prompted, at a standard day and time that they select themselves, to fill in a short assessment via smartphone. This type of monitoring is increasingly used to assess interventions, amongst others because it results in more ecologically valid results, is sensitive to change, and can be used to determine how variables relate to each other across time and contexts. Self-monitoring in psychosis has repeatedly been found to be feasible, with many studies using about 60 items (assessed in 2-3 minutes) that are presented 10 times per day for at least a 6-day period.74 From baseline to 6-month follow-up all participants in this study assess social functioning, adversities and revictimization (17 items, 1,5 minutes) once per week. The RoQua web platform will be used for the smartphone assessments. RoQua is an online questionnaire application developed at the University Medical Center Groningen (UMCG) in cooperation with several large mental health care institutions from The Netherlands. The web application sends out a text message with a link. Via this link, participants can access the platform on which the assessment can then be conducted. The platform is only used for sending out questionnaires, collecting answers and data-storage. Participants do not receive any feedback on their answers. The outcomes of two of the questionnaires can be used by therapists to assess the progress of a participant in an intervention as part of the therapy protocol (see section 5 Treatment of subjects). RoQua is hosted in data centres of the University of Groningen (UG), and operates entirely in compliance with the NEN-ISO/IEC 27001 standard and the EU General Data Protection Regulation (GDPR). All sessions with the web application are secured with SSL. HL7 traffic is shielded with VPN between the users and the RoQua server clusters.

Outcomes that are assessed weekly from baseline to 6-month follow-up are:

- Social functioning: with 2 items adapted from time use survey, ^{75,76}
- Adversities: using the 7-item TTIP Adverse Events Questionnaire.²²
- Revictimization: using the 8 interpersonal victimization items from the TALE.

Daily monitoring: to assess how post-traumatic stress and psychosis dynamically interact at baseline and post-treatment.

As part of the baseline and post-treatment assessment participants are asked to monitor post-traumatic stress and psychosis symptoms once per day for the duration of two weeks (49 items, 4-minutes). This is optional and participants will be randomized regardless of whether they will do the daily monitoring. Factors that are assessed via the RoQua platform are: re-experiencing (5 items, 0 - 4 rating),⁴⁶ avoidance (2 items, 0 - 4 rating),⁴⁶ negative cognitions and mood (7 items, 0 - 4 rating),⁴⁶ hyper arousal (6 items, 0 - 4 rating),⁴⁶ beliefs about self/beliefs about others (9 items, 1-7 rating),⁴⁷ dissociation (4 items, 0 - 4 rating),⁴⁸ control (3 items, 1 - 7), ⁴⁹ hallucinations (3 items, 1 - 7 scale), paranoia (3 items, 1 - 7),^{50,51} and involuntary memory characteristics (7 items, 1 - 7 rating).⁶⁰

TABLE 1 Overview of the instruments used at the different time-points.

Recruitment assessment

Demographic characteristics

Trauma and Life Event Checklist (TALE)

Clinician Administered PTSD Scale (CAPS-5)

Psychotic symptom rating scales (PSYRATS)

Enriched Social Support Instrument (ESSI)

Baseline and follow-up assessments

Clinician Administered PTSD Scale (CAPS-5)

PTSD Checklist for DSM-5 (PCL-5)

The International Trauma Questionnaire (ITQ)

Trait Dissociation Screening Questionnaire – short version (TDQ-s)

Brief version of the Posttraumatic Cognitions Inventory 9-item (PTCI-9)

Beck Depression Inventory II (BDI-II)

Green et al. Paranoid Thought Scales (GPTS)

The Voice Impact Scale (VIS)

Auditory Hallucination Rating Scale, 3-item frequency subscale (AHRS)

The Brief Resilience Scale (BRS)

The Questionnaire about the Process of Recovery (QPR)

Arizona Sexual Experience Scale and sexual autonomy scale (ASEX, SAS)

Cost-effectiveness (TiC-P and EQ-5D)

Other assessments

Weekly monitoring of social functioning, adversities and revictimization (baseline to 6-month follow-up)

Daily monitoring at baseline and post-treatment (optional)

Personal views on TFT and influence on recovery (in subgroup)

